## **PART I – REPORT OF PRIOR INVESTIGATIONS**

### **1. General Introduction**

#### **Overview of disorder studied, and current treatments**

Spinal cord injury (SCI) is an insult to the spinal cord resulting in a change, either temporary or permanent, in its normal motor, sensory, and/or autonomic function. It is estimated that the annual incidence of spinal cord injury (SCI), not including those who die at the scene of the accident, is approximately 40 cases per million population in the U. S. or approximately 12,000 new cases each year.

SCI primarily affects young adults. As the average age of the population in the United States rises, the average age of the spinal cord injury increased from 28.7 years in the 1970's to 41 years as of 2005. In addition, advances in the chronic care of people with spinal cord injury have significantly increased their life expectancy. As a result, the number of people in the United States who are alive in 2012 who have SCI has increased to a 270,000 persons, with a range of 236,000 to 327,000 persons.

[figure not shown]
Persons with tetraplegia have sustained injuries to one of the eight cervical segments of the spinal cord; those with paraplegia have lesions in the thoracic, lumbar, or sacral regions of the spinal cord. Since 2005, the most frequent neurologic category at discharge of persons reported to the database is incomplete tetraplegia (40.8%), followed by complete paraplegia (21.6%), incomplete paraplegia (21.4%) and complete tetraplegia (15.8%). Less than 1% of persons experienced complete neurologic recovery by hospital discharge (National Spinal Cord Injury Database, 2012).

#### **Previous Work**

In a study published in Nature by Hochberg, et al tetraplegic participants were implanted with a 96-channel microelectrode array in the cortex. Movement intentions from neural activity were decoded from the microelectrodes and used by tetraplegic participants to successfully operate a robotic arm by their thoughts. The microelectrode array is a multichannel, high-density, device that allows neural recordings from large populations of neurons. Over the past two decades, this patented microelectrode array technology has undergone numerous refinements and repeated validations in a variety of species (humans, monkeys, birds, rodents, felines, fish) and

preparations (in vitro and in vivo). This effort delivered a proven and well-documented method to obtain stable and long-term neural recordings of action potentials (spikes) and field potentials in brain and peripheral-nerve tissue. Because the array can be wired to various connector types, researchers can choose a connector that is optimal for chronic (long-term) or acute (short-term) recordings from small to large participants as well as from slice and cell culture preparations (Blackrock Microsystems).

Battelle, (a private nonprofit applied science and technology development company headquartered in Columbus, Ohio) was directly involved with the Hochberg study referenced, and specifically developed the decoding algorithms used in four of the participants (Bouton 2009), and has now developed a technology called “Neural Bridge” to link neural decoding to neurostimulation (Bouton 2011, Bouton et al, 2016, Sharma et al, 2016). Specifically, Battelle has developed a technology that decodes brain activity for imagined movements and then transforms the data into neuromuscular stimulation patterns to evoke the limb movement that was imagined. This technology in effect creates a ‘neural bridge/bypass’ or ‘virtual spinal cord’ to bypass injured or degenerated pathways. This technology can target specific muscles in the forearm, for example, to allow wrist and hand/finger movements based on the decoded brain activity in the participant’s motor cortex. The objective of the study proposed in this submission is to allow reanimation of a paralyzed limb under complete voluntary control of the participant. This will be a significant step towards the artificial spinal cord / nervous system with potential applications beyond spinal cord injury, including stroke and motor neuron disease. See Figure 1 for an overall system diagram and neuromuscular sleeve and glove components of the system. The Neuroport device is a (510(k) K070272, K090957) cleared device manufactured by Blackrock Microsystems (Salt Lake, Utah) and the Neuromuscular Stimulator System is an investigational device developed by Battelle (Columbus, Ohio) that has been reviewed by a registered IRB and has been used with human participants with no related adverse effects reported. (See the Device Description section for further details.)

**Figure 1. a) Overall Neural Bridging System Diagram; b,c) Neuromuscular stimulation sleeve and glove**

### Study Rationale

This study will extend the previous work in neural decoding and allow the investigators to better understand how the human nervous system can be augmented or bridged when trauma or disease has occurred which decouples the nervous system from the voluntary control of muscles.

Previous work allowed participants to imagine various limb movements and control a computer cursor or other devices (Bouton 2009). The key extension in this study is to allow participants with tetraplegia to regain voluntary control of a paralyzed limb. The system will use re-coding algorithms to first decode brain activity in the motor cortex and then re-encode the signals for high definition stimulation of the selected muscles. “Neural bridging”, as it is termed, involves signal monitoring (in the nervous system with a Neuroport microelectrode array), decoding of the information present, and then re-encoding appropriate stimulation signals for non-invasive insertion in another location in the nervous system, in this case directly to the muscles of interest. The insertion of signals back into the nervous system will be achieved through a non-invasive function neuromuscular stimulation system (NMES) (Bouton et al 2012). The NMES will be in the form of a cuff/array or a sleeve consisting of a flexible circuit that has electrodes of 12mm diameter. In the case of the sleeve, the cuff and electrodes are housed in a spandex fabric. A non-toxic FDA-approved conductive lotion forms the interface between the electrodes and the skin allowing stimulation of small and large muscles in the arm and hand to evoke a wide variety of movements. The optional glove (Figure 1, b and c) connects to the sleeve and provides information back to the system about the position of the hand and arm in space, as well as the flexion and extension of the fingers and wrist. The glove does not provide stimulation and is for positional information gathering only.

Neurostimulation systems have been developed to restore functional movement in chronic paralysis population. The approach that provides the most functional multidimensional movement control utilizes a combination of a brain-computer interface (BCI) with implanted cortical sensors. However, to date, human applications of implanted BCI technology have been limited to assistive technologies such as power chairs or robotic arms. An implanted BCI neuroprosthetic system designed to produce functional upper limb movement was only recently tested in an animal.

The system described in this study is unique in that the BCI system translates intended action into human motion. Unlike the animal study previously referenced where the functional movement was generated through an implanted functional electrical stimulation system, this study will deliver surface stimulation through the NMES.

## **Team Expertise**

This investigation will be conducted at the Neuromodulation Center at The Ohio State University. This Center represents a collaborative effort between faculty in the Departments of Neurological Surgery, Neurology and Physical Medicine and Rehabilitation. The OSU functional neurosurgery team led by the PI, [name] is internationally renowned for expertise with functional and stereotactic neurosurgery, [name] surgical team has performed over 2,500 neurological system implants in the past 16 years for various neurological, chronic pain and other applications.

The study participants will be recruited from the Spinal Cord Injury Rehabilitation Service, which is a CARF accredited spinal cord injury rehabilitation program within the Department of Physical Medicine and Rehabilitation (PM&R). The PM&R program at OSU is nationally recognized as a preeminent rehabilitation program. [name] is the Chair of PM&R and a study co-investigator.

Battelle has extensive experience in developing commercial medical products for human use and in neural decoding in paralyzed human participants (Bouton 2009). Battelle has also developed training methods to enhance the ability of participants to evoke targeted neural activity in the primary motor cortex for various imagined arm and hand movements. Battelle has also tested the study components (cuff, sleeve, conductive lotion and stimulator system) in a Battelle IRB-approved Study (Battelle IRB 0466) without adverse effects or complications.

## **PART II - INVESTIGATIONAL PLAN**

### **1. Investigational Purpose**

The purpose of this clinical study is to allow the investigation of the Neural Bridging System for participants with tetraplegia to assess if the investigational device can reanimate a paralyzed limb under voluntary control by the participant's thoughts.

## **2. Protocol Overview and Design**

The target population will be people with C4-C6 ASIA A spinal cord injuries (motor and sensory complete neurologic injuries) who are more than 1 year post injury and who are neurologically stable.

## **3. Protocol Specifics**

### **3.1 Participation Criteria**

This study will plan to enroll up to 5 participants who have been diagnosed with tetraplegia. Study participants will be persons of any race, ethnic group, or gender. Participants who enter will be free to withdraw from the study at any time without affecting their access to other treatments at OSU and affiliated hospitals. The first 5 eligible and consenting participants will be accepted into this study. No gender or minority is intended to be excluded. However, since the sample size is small, there may be inadequate representation of ethnicities, genders, and race in the study sample.

#### **3.1.1 Inclusion and Exclusion Criteria**

##### **Inclusion Criteria:**

- Must be 21 years or older.
- Must be tetraplegic (C4- C6 ASIA A)
- 12 months post injury and neurologically stable
- Participant is willing to comply with all follow-up evaluations at the specified times.
- Participant is able to provide informed consent prior to enrollment in the study.
- The participant is fluent in English.
- Participant must have a caregiver willing to participate in the study who will provide care for the surgical site.

##### **Exclusion Criteria:**

- No active wound healing or skin breakdown issues.
- No history of poorly controlled autonomic dysreflexia.
- Medical contraindications for general anesthesia, craniotomy, or surgery.
- Diagnosis of acute myocardial infarction or cardiac arrest within previous 6 months.

- Participants with any type of destruction and/or damage to the motor cortex region as determined by MRI.
- Dementia
- Psychiatric disturbances
- Other implantable devices such as heart/brain pacemakers
- Participants who rely on ventilators
- Co-morbid conditions that would interfere with study activities or response to treatment, which may include:
  - Life expectancy < 3 years
  - Severe chronic pulmonary disease
  - Confirmed seizure disorder that requires continued clinical care
  - Local, systemic acute or chronic infectious illness
  - Life threatening cardiac arrhythmias
  - Severe collagen vascular disorder
- Kidney failure or other major organ system failures History of a neurological ablation procedure.
- Labeled contraindication for MRI.
- History of hemorrhagic stroke.
- History of HIV infection or ongoing chronic infection (such as tuberculosis).
- Pregnant or of child-bearing potential and are not taking acceptable methods of contraception.

Participation in another investigational device or medication trial

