## **4. Risk Analysis**

### **4.1 Risks**

The surgical risks for implantation are the same as for any intracranial craniotomy, image guided procedures and implantable device such as a deep brain stimulator or a motor cortex stimulator procedure. This includes hemorrhages (intraparenchymal, subdural or epidural hematoma), paralysis, coma and/ or death, stroke, leaking of fluid surrounding the brain, seizures, infection, allergic reaction, temporary or permanent neurological complications, confusion or attention problems, pain at the surgery sites and headaches.

Training and therapeutic sessions involving BCI regulated functional electrical stimulation will need to be monitored for autonomic dysreflexia signs and symptoms.

As with any muscle stimulator, there can be a risk of excessive current and skin irritation or burns. The stimulator in the Neural Bridging System, however, limits the average output current density to less than  $2\text{mA/cm}^2$  at the skin and the average power density to less than  $0.25\text{W/cm}^2$  to provide safe levels and avoid tissue damage. Despite these built-in safety limits, current and power density could exceed FDA guidelines if electrodes lift off the skin. This has the potential to cause causing minor irritation or first degree burns locally. The research investigator will monitor frequently during test sessions for wrinkles and misalignment of the sleeve, and any signs of electric shock, skin irritation, and/or burns.

The sleeve material itself is spandex, with registration marks printed on it. The material itself has been formally tested for biocompatibility, both in vitro and in vivo, prior to printing and laundering. The printed, laundered sleeve was tested in Battelle's IRB-approved Able-bodied study for up to 8 hours, with and without similar nontoxic conductive lotion. No adverse skin

reactions were observed. The investigator, who will already be monitoring frequently for signs of irritation from electric shock, will also monitor for signs of allergic skin reaction.

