#### **4.2 Procedures for Minimizing Risks**

Investigators involved with this study have a great deal of expertise with the management of tetraplegic patients and with craniotomies. The surgical team has over 16 years of experience with deep brain stimulation implants with over 1600 DBS implants for various indications. The study inclusion/exclusion criteria have been developed to select those who would most likely benefit from this study as well as excluding those with higher risks. Study participants will be monitored after surgical implantation in neurosurgical and physiological monitoring units with personnel experienced in the care of complex neurosurgical participants and monitoring neurological status. In the case of cerebrospinal (CSF) leakage or pain, patients will be managed per the standard clinical practice. In case of infection that is not responsive to antibiotic treatment or allergic reaction to the implanted device, the device will be explanted.

Upon completion of the study, participants will have the entire cortical implant system surgically removed. The procedure for removing the device is similar to those of the implant procedure.

Risks for removal are similar to insertion: infection, bleeding, need for further surgery, and seizures.

Post-surgical removal the participants will be asked to come for post-surgery follow up appointments to remove stitches/sutures and wound caring.

Risks are minimized in all of the non-surgical procedures including blood drawing and the neuroimaging procedures by having trained and highly experienced personnel performing all those tasks.

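### Two lines in the exclusion list carry a stray negative, so as written they exclude people without the named conditions and do not exclude people with them

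*Combined protocol and SAP*

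**What the plan says.** Section 3.1.1 of the combined protocol and SAP has an inclusion list followed by a list headed "Exclusion Criteria". The first two lines of the second list are "No active wound healing or skin breakdown issues" and "No history of poorly controlled autonomic dysreflexia". The next line is "Medical contraindications for general anesthesia, craniotomy, or surgery", and a later one is "History of hemorrhagic stroke".

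Section 4.2 states what the criteria are for: "The study inclusion/exclusion criteria have been developed to select those who would most likely benefit from this study as well as excluding those with higher" (the quotation stops just before the sentence's closing word, which refers to risk). Section 4.1 names hazards to which the two lines relate. On the stimulator it says: "As with any muscle stimulator, there can be a risk of excessive current and skin irritation or burns". On autonomic dysreflexia it says that stimulation sessions "will need to be monitored for autonomic dysreflexia signs and symptoms". It also lists infection among the surgical risks.

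**The concern.** An item under an exclusion heading removes the person who meets it. A candidate with intact skin meets the first line as written, and a candidate with no history of badly controlled dysreflexia meets the second. Both would be excluded. A candidate with a skin problem, or with such a history, meets neither line and is not excluded by them.

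This is operative eligibility text, and it touches hazards that the protocol itself names. The hazard table in Section 4.5.1 also counts certain protocol exclusions as risk controls. It does not cite these two lines, but it shows that the list is meant to work as a safety control and to be applied as written.

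**Working it through.** No arithmetic applies. The point does not depend on an error rate, power, effect size or sample size, and the documents state no sample-size calculation. The check is one of wording and logic.

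**Step 1: direction of each item.** Under an exclusion heading, an item that states condition X excludes people with X. An item that states *No* X excludes people without X and leaves people with X untouched.

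| Item in the exclusion list (Section 3.1.1) | Who is excluded as written | Agrees with the aim in Section 4.2? |
|---|---|---|
| "No active wound healing or skin breakdown issues" | People without a wound or skin problem | No |
| "No history of poorly controlled autonomic dysreflexia" | People without that history | No |
| "Medical contraindications for general anesthesia, craniotomy, or surgery" | People with a contraindication | Yes |
| "History of hemorrhagic stroke" | People with that history | Yes |

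The second and fourth rows are the clearest comparison. Both are history items in the same list; one carries the negative and the other does not.

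**Step 2: other negatives in the list.** The contraception item also contains a negative, but it is correct there, because lack of contraception is the excluding condition. The remaining items all name something whose presence excludes. Exactly two lines are reversed.

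**Step 3: is it corrected elsewhere?** The inclusion list mentions neither condition. Sections 4.1, 4.1.1 and 4.2 discuss risks, withdrawal and risk reduction, but none of them restates the two criteria in the intended direction. The monitoring statement in Section 4.1 shows that dysreflexia is a recognised risk; it does not settle the wording of the criterion.

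**Step 4: do other criteria cover the same people?** Partly. Surgical contraindications, infectious illness, and the open-ended class of co-morbid conditions that would interfere with the study could remove some candidates with wounds or uncontrolled dysreflexia. None of these items names either condition, so the cover is incomplete and depends on judgement.

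**Step 5: against the stated aim.** Section 4.2 says that the criteria exclude people at higher risk. The literal effect of the two lines is the opposite, so the conflict is visible from the document alone.

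**The case against.** The strongest reply is that nobody would be misled. Applied literally, the two lines would turn away the healthiest candidates at once, so a screener would notice the slip immediately. Section 4.2 makes the intent plain, and Section 3.2.1 requires a medical history review and a physical and neurological examination before surgery. This stands, and it is why the chance of a wrong enrolment is small. It does not make the text right: safety-related eligibility wording should not depend on the reader reversing it.

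Four stronger readings are tempting, and the documents do not support them.

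- **That the plan intends to enrol such people, or admits them.** It does not. Failing to meet one exclusion admits nobody, and the other criteria still apply. The most that can be said is that these two lines do not exclude them.
- **That the eligibility checklist is reversed.** Case report forms are listed as Appendix 2, and Section 5.1 says paper forms are used, but the forms were not available for review. Whether they copy this wording, or score it as yes or no, is unknown. A reversed checklist is an assumption.
- **That the harm can be sized from the cap of five participants.** One person out of five is a share of the cohort if an error occurs. It carries no probability of the error, and it would be the same for any misapplied criterion.
- **That all enrolment is at stake.** Section 3.2.3 refers in the present tense to participants already receiving stimulation, so at least one person is already in Phase III. The wording can affect only places still to be filled, and their number is not given.

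**Conclusion.** The point holds as a drafting error. Two lines of the exclusion list are wrong as written, contrary to the rest of the list and to the aim in Section 4.2, and nothing elsewhere corrects them. It was evidently not a deliberate design decision.

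Its practical size is small and cannot be expressed as a number. Endpoints, analysis and error rates are unaffected. The conclusion rests on the text of Section 3.1.1 and on the ordinary meaning of an exclusion list. Any consequence for screening records further assumes that the eligibility form repeats the wording. The correction is still worth making, because a reader who followed the list exactly would exclude the wrong people.

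**What to change.** Reconcile the heading and the two lines. Two repairs are equally consistent with the evident intent: delete *No* from both lines and leave them in the exclusion list, or move both lines unchanged to the inclusion list. Either one aligns the text with Section 4.2 without adding a new criterion.

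Then check that the eligibility form scores both lines in the intended direction.

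The cost is one word in each of two lines, or the relocation of two lines, plus a check of one form. No analysis or sample-size text needs to change.

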### **3.1.2 Informed Consent**

Informed consent will be obtained by the PI or their designee with documented specific knowledge of the study. The informed consent form will be reviewed with the participant and all questions will be addressed before the participant signs the consent form. The participant will also be given a copy of the signed consent, and a copy of the consent will be placed in the patient's medical record.

### **3.2 Study Phases**

The study design will consist of the following four (4) phases listed below.

- I. Baseline (approximately 8 weeks prior to surgery)
- II. Surgery (approximately 1-2 weeks)
- III. Decoding and stimulation (approximately 60 months)
- IV. Follow-up (approximately 8 weeks post device explantation)

